4.6 Statistical Analysis for the Immune Sub-Study

Seroconversion will be estimated and compared to licensure data using binomial tests. Antibody levels in pregnancy will be compared to licensure data for the relevant vaccine and dose using one-sample t-tests. We will stratify by gestational age, participant age, and other co-factors that might influence immune response. Maternal antibody levels will be compared to infant levels at birth, controlling for infant gestational age at delivery, birth weight, and infant feeding. Exploratory analysis of antibodies in breast milk will be compared to maternal serum antibody levels.

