4.3 Sample and Data Collection for Immune Sub-Study

Maternal blood samples will be collected pre- and post-vaccination. We anticipate study visits occurring 4 weeks up to vaccination, four weeks after vaccination, and again twelve weeks after vaccination. Maternal blood samples will also be collected at delivery. We anticipate these study visits to occur +/- 2 days at delivery, and 4-6 weeks after delivery. If the delivery sample is within the window of another collection time point, we will collect only one sample. SARS-CoV-2 serology will be performed for all maternal samples to determine IgG seropositivity rate and semi-quantitative antibody levels to anti-spike protein. IgG class sub-typing will be performed on maternal samples. Additionally, serology for IgG and IgA antibodies will be performed on selected maternal blood samples. Cord blood samples at delivery and infant blood samples at 4-6 weeks post-delivery will be collected and analyzed on serologic assays and compared to peripartum maternal antibody levels.

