4.5 Statistical Analysis and Metrics

To adequately power for comparisons of adverse events, we used estimates of vaccine-related adverse events (i.e. pain at injection site, redness, swelling, fever, fatigue, chills, headache, muscle pain, joint pain, grade 4 serious adverse events) from the subset of younger participants in the Pfizer vaccine trial, as an example (12). The rate of overall adverse events was 25%, and with a sample size of 451 in the vaccinated cohort we could estimate this prevalence with $\pm 4\%$ precision and 95% confidence. Sample sizes are highly feasible and will allow for comparison of adverse obstetrical and infant outcomes between vaccinated and unvaccinated participants. Given a sample size of 500 per group (vaccinated vs. unvaccinated) we would have 80% power to detect a minimum relative risk of 1.5.

The immunogenicity sub-study would require 89 participants, assuming 10% loss to follow up to estimate a 70% seroconversion rate with \pm 10% precision and 95% confidence. A seroconversion rate closer to 80% would require 68 participants. For comparisons of antibody levels, using estimates for the 18-55y age group (13) we would need approximately 48 participants to demonstrate a 10% difference in geometric mean titer with 95% power and assuming an attrition rate of 10% per visit.

The presence of any adverse outcomes (vaccine and pregnancy-related) will be compared between vaccinated and unvaccinated using time-varying Cox's proportional hazards models (14), stratified by vaccine type, and including important confounders. Effectiveness will be assessed descriptively through participant reporting of positive SARS-CoV-2 tests and COVID-19 diagnoses in vaccinated

and unvaccinated participants. Clinical features of breakthrough cases will be described in those vaccinated. Exploratory analyses will investigate differences between vaccinated and unvaccinated people. Clinical severity will be compared with unvaccinated people in the CANCOVID-Preg cohort. This will include tracking of infections with variants of concern where possible in both vaccinated and unvaccinated participants.

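### Section 4.6 tests immunogenicity against licensure values as if they were known exactly, and the 89 makes no allowance for participants already seropositive

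*Protocol*

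**What the plan says.** Protocol section 4.6 names two tests for the immune sub-study. For the binary endpoint: "Seroconversion will be estimated and compared to licensure data using binomial tests". For the continuous one: "Antibody levels in pregnancy will be compared to licensure data for the relevant vaccine and dose using one-sample t-tests". It gives no sample size or standard error for the licensure values. It also plans stratification by gestational age, participant age and further unnamed co-factors.

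Section 4.5 gives the sizing: "The immunogenicity sub-study would require 89 participants, assuming 10% loss to follow up to estimate a 70% seroconversion rate". The half-width there is 10 points at the 95% level, and the number falls to 68 if the rate is nearer 80%. For antibody levels the section asks for about "48 participants to demonstrate a 10% difference in geometric mean titer with 95% power and assuming an attrition rate of 10% per visit".

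Section 4.3 plans maternal samples before and after vaccination, from which it will determine IgG seropositivity and "semi-quantitative antibody levels to anti-spike protein".

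On who enters, section 3.2 requires a minimum age of 19 and a pregnancy that began in 2023. Section 1.3 opens the sub-study to British Columbia participants who can provide samples and plan a COVID-19 vaccination in pregnancy. Neither section excludes earlier doses, earlier infection or existing anti-spike antibody. Section 4.2 collects COVID-19 history, number of doses and dosing interval. The protocol does not define seroconversion.

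**The concern.** There are two separate faults.

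1. **The reference is treated as exact.** A licensure geometric mean titre or seroconversion rate is an estimate from a finite sample. A one-sample t-test or binomial test sets its sampling error to zero. The p-value is then too small and the interval for the difference too narrow, so a chance deviation in the reference can be read as an effect of pregnancy. Immunogenicity is one of the listed primary objectives, and section 4.7 sends results to public health partners monthly.

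2. **The number evaluable for seroconversion.** Anti-spike IgG is raised both by infection and by spike-based vaccines. People who became pregnant in 2023 and were not screened for prior exposure may already be positive. On a negative-to-positive definition they cannot seroconvert. If they leave the denominator, precision falls. If they stay in it, the rate is pulled down relative to a reference population without such exposure.

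**Working it through.** **Plan's own figure first.** Inputs from section 4.5: rate 0.70 (or 0.80), half-width 0.10, 95% confidence, 10% loss.

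- n = 1.96² × p(1 − p) / 0.10².
- p = 0.70: 80.67; × 1.1 = 88.7, so 89. Dividing by 0.9 instead gives 90.
- p = 0.80: 61.46; × 1.1 = 67.6, so 68. Dividing by 0.9 instead gives 69.

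The 89 and 68 reproduce. Completers from 89: 89 × 0.9 ≈ 80.

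**Fault 1: type I error with an estimated reference.** Assumptions: two-sided 5% (section 4.6 states no level; this matches the 95% confidence in section 4.5), equal standard deviation in study and reference, and no true difference. With n participants and a reference of m people, the variance of the difference is larger than the test assumes by the factor 1 + n/m. Hence

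true type I error = 2[1 − Φ(1.96 / √(1 + n/m))].

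Example, n = 80 and m = 200: √1.4 = 1.183; 1.96/1.183 = 1.657; result 0.098.

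The reference size m is not in the protocol; the range is assumed.

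| m | t-test, n = 80 | t-test, n = 48 | exact binomial, n = 80, p = 0.70 |
|---|---|---|---|
| 30 | 31% | 22% | 30% |
| 50 | 22% | 16% | 22% |
| 100 | 14% | 11% | 14% |
| 200 | 10% | 8% | 8.9% |
| 500 | 7% | 6% | 6.1% |
| 1000 | 6% | 6% | 5.2% |
| 5000 | 5.2% | 5.1% | not run |

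The binomial column is an exact enumeration over the reference count. With a truly fixed reference that test rejects 3.7% of the time, because it is discrete. Simulation of the t-test at n = 48 agrees with the formula (22.4% at m = 30; 5.9% at m = 500 against 6.1%). If 48 is the number before attrition, fewer are analysed and the excess is smaller: with 35 left after three visits (48 × 0.9³), 18%, 13%, 9% and 7% at m = 30, 50, 100 and 200.

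**Fault 2: half-width when some completers are already seropositive.** Assume a negative-to-positive definition and a share s already positive (not given in the protocol). Half-width = 1.96 × √(0.21 / (80(1 − s))). Enrolment to keep ±10 = 81 / (1 − s) / 0.9.

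| s | evaluable | half-width (points) | enrolment to keep ±10 |
|---|---|---|---|
| 0 | 80 | 10.0 | 90 |
| 10% | 72 | 10.6 | 100 |
| 25% | 60 | 11.6 | 120 |
| 50% | 40 | 14.2 | 180 |
| 75% | 20 | 20.1 | 360 |

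If those already positive are instead kept and counted as non-converters, the expected rate falls. With s = 25% it is 0.70 × 0.75 = 52.5%, which would look like a deficit against a 70% reference.

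**The case against.** The best defence is that neither size can be read from the protocol. With a reference in the thousands, the sampling-error fault almost vanishes (5.2% at m = 5000), and the exact binomial test is already close to 5% at m = 1000. The publication cited for sizing antibody levels is not named as the licensure comparator, and its sample size is not given, so it cannot be used to argue for a small m. This stands: the direction is certain, but the size is not.

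A reader might also infer that the ±10% is simply not delivered. The documents do not support that. The 89 is arithmetically sound, no baseline seropositivity is stated, and a definition based on a rise from the pre-vaccination sample would keep seropositive participants evaluable. The missing definition may be supplied in a statistical analysis plan that is not at hand, and is not counted as an error here.

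Nor is the first fault a cause of the second: one-sample testing does not change the half-width of the seroconversion estimate.

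Three other strong readings also fail.

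- **The pre-vaccination sample goes unused.** Seroconversion implies a before-and-after comparison, and section 4.6 does not rule that sample out.
- **The assays are on different scales.** The protocol names neither assay, so comparability is a condition to check.
- **The whole immunogenicity objective becomes uninterpretable.** Antibody levels over time and the maternal–infant and breast-milk comparisons do not depend on the licensure test.

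Matching on vaccine and dose and stratifying by co-factors help in part. However, neither carries the reference's standard error, and neither names baseline serostatus or prior infection.

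**Conclusion.** The point holds in two limited parts.

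First, the tests fixed in section 4.6 ignore the uncertainty of the licensure values, so their true type I error lies above what a fixed reference would give. For the t-test with 80 participants the excess runs from large (31% at an assumed 30 reference subjects) through moderate (10% at 200) to negligible (5.2% at 5000). This rests on equal standard deviations and a two-sided 5% level. A comparison that includes the reference's standard error is right at any reference size.

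Second, the 89 and its ±10 points assume that every completer can seroconvert, while eligibility does not ensure this. On a negative-to-positive definition, the half-width at 70% is ±10.6, ±11.6, ±14.2 or ±20.1 points for an assumed 10%, 25%, 50% or 75% already seropositive. This part is conditional on both the definition and the share.

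**What to change.** **Licensure comparison (section 4.6).** Replace the one-sample t-test with a Welch comparison on log titre, and the binomial test with a two-proportion comparison. Use the published standard error and sample size of the licensure data; where only a 95% interval for the geometric mean titre is published, SE = (ln upper − ln lower) / 3.92. Where assay units or prior exposure are not comparable, present the two results side by side without a test. No common assay need be required, since that could mean extra laboratory work.

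*Cost:* wording, plus extraction of the published figures. Intervals for the difference widen by the factor √(1 + n/m): with n = 80, by 61% at m = 50, 18% at m = 200 and 0.8% at m = 5000.

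**Seroconversion (sections 4.5 and 4.6).** Use the pre-vaccination sample already planned in section 4.3 to classify baseline serostatus. Report seroconversion among those seronegative at baseline, with that denominator stated. For the others, report fold rise from baseline as a supplementary estimate. It should not replace the main comparison, because it shows whether participants respond to the dose, not whether the response matches licensure populations. State the ±10% as conditional on the number evaluable.

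*Cost:* wording only, with no new samples. The seroconversion interval may be wider than ±10 points unless enrolment rises as tabulated above.

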4.7 Knowledge Translation

Analysis and reporting from this project will be ongoing, as data become available. We will produce regular monthly national reports for distribution to our national and provincial public health partners and through the additional networks of the CANCOVID-Preg members. These reports will also be publicly shared, including with study participants, via our website, social media channels, and traditional media outlets. A knowledge broker will be engaged as part of the team to optimize translation of our findings to public health officials and a diverse range of the Canadian population, and to enhance translation of these findings into clinical guidance and public knowledge. In addition, we will leverage our partnerships with pan-Canadian university communications departments to expand the reach of our recruitment and knowledge translation outputs. Finally, our team includes clinician and policy knowledge users who will be active in the interpretation and dissemination of results, including amongst professional organizations that influence vaccine recommendations (e.g. SOGC).

REFERENCES

- 1. World Health Organization. Weekly Operational Update on Covid-19 -19 April 2021 (Accessed April 20, 2021). https://www.who.int/publications/m/item/weekly-operational-update-on-covid-19---19-april-2021.
- Government of Canada. Coronavirus diseases (SARS-COV-2): Outbreak Update. (Accessed April 20, 2020). https://www.canada.ca/en/public-health/services/diseases/2019-novel-coronavirus-infection.html#a1.
- Canadian Surveillance of COVID-19 in Pregnancy: Epidemiology M, and Infant Outcomes. Report #3: Maternal and Infant Outcomes (March 1, 2020 to December 31, 2020) from Five Canadian Provinces. 2021.
